6.3. Treatment Compliance

Patients will be dosed at the research site under the supervision of at least 1 physician, in the presence of a psychiatrist and therapist.

6.4. Patient Numbers

Patients will be assigned a patient number at screening, after they have signed the informed consent form (ICF). This patient number will be the primary patient identifier throughout the duration of the study. Each patient will be assigned a unique number in the order in which they are entered into the study. Once a patient number has been allocated, it must not be reassigned to another patient. If a patient does not meet the entry criteria (screen failure), they may be rescreened at the discretion of the Investigator and medical monitor. Rescreened patients will be assigned a new patient number.

6.5. Randomization and Blinding

This is an open-label study; all patients will receive BPL-003.

6.6. Study Visits

The study visits are outlined below. Study visits and procedures are also detailed in the Schedule of Events in [Table 1](#).

- **Screening:** Patients will be screened up to 14 days before their psychedelic preparation session to confirm their eligibility for the study.
- **Abstinence:** Patients will be expected to have no HDD at least 72 hours prior to dosing and no alcohol at all in the 24 hours prior to dosing. If breath alcohol is not zero on dosing day, patients may reschedule once if they are deemed not to have completely relapsed; however, if they fail the second time, they will be excluded from the study.
- **Psychedelic Preparation Sessions:** Following the initial Screening Visit, all patients will participate in 3 preparatory sessions over approximately 2 weeks before being dosed (patients should not undertake preparation sessions if intoxicated, as recommended by published guidance on the conduct of studies of psychedelic compounds) ([Johnson, 2008](#)). Investigator discretion to be applied where patient has some alcohol in their system, but is still able to absorb the information and build a therapeutic alliance. The aim will be to establish a therapeutic alliance during the preparatory sessions so that patients will be well prepared for the BPL-003 treatment session and receive ongoing AUD relapse prevention psychotherapy. The psychedelic preparation session will be audio recorded for safety and quality assurance purposes.
- **Dosing Visit:** After completion of the 3 preparatory sessions, patients will attend the clinical study facility for their dosing visit. Patients will be resident at the clinic from the morning of Day 0 (dosing day) until approximately 4 hours postdose.
 - BPL-003 will be administered to patients in the designated setting, in accordance with published guidelines for clinical trials of psychedelic compounds ([Johnson, Richards and Griffiths, 2008](#)), with particular emphasis on 'set' (the subject's mental state prior to dosing) and 'setting' (the dosing environment). The psychedelic therapist will remain with patients while patients are in an altered state of consciousness.
 - During the dosing session, the therapist will be supportive and non-directive, and not attempt to influence the patient's psychedelic experience. Site staff will be trained to maximise patients' psychological welfare during dosing and the subsequent psychedelic experience (e.g., assessments will be performed with as minimal interruption as possible;

patients will be encouraged to lie down during dosing). All psychological support providers will be trained in accordance with the therapy manual.

- All dosing sessions will be audio/video recorded for safety and quality assurance purposes
- After return to a usual state of consciousness after dosing, patients will be asked to have a one-to-one guided qualitative interview with independent researchers trained in microphenomenology methods to discuss their psychedelic experience (as detailed in the Qualitative Interview Study Manual). This will be done either face to face at the clinic or via video call. Clinical research measures will then be administered to provide quantitative measures of the patient's psychedelic experience.
- After dosing, the patients will have to remain at site for at least 4 h. Patients may be discharged 4 h after dosing, provided the Investigator or psychiatrist determines that it is safe for the patient to leave, having assessed their individual psychological wellbeing. All patients will have their "readiness for discharge" (see Appendix) assessed every 30 min starting 90 min after dosing. If the patient is not ready for discharge at 4 h post dose, then the questionnaire will be repeated when the Investigator believes the patient may be ready for discharge.
- If the study team considers that a patient may pose a risk to themselves or others, they may be prevented from leaving the site. Patients will be informed of that possibility, and consent to it, at Screening. Any actions taken to minimise a participant's risk to themselves or others and/or prevent them from leaving the site will be undertaken in accordance with appropriate legislation.
- In the event of extreme distress unresponsive to any intervention, or in the event of threatened or actual violence, rescue medication will be given in liaison with medical staff at the site. The medication of choice is a short acting benzodiazepine given orally and therefore follows established National Institute for Health and Care Excellence (NICE) guidelines for rapid tranquilisation. Oromucosal midazolam or lorazepam injection will be given as a first line treatment. Any further treatment will follow NICE guidelines. Rescue medication will be given under the supervision of a psychiatrist. . If rescue medication is given, patients may need to stay at the site for longer than scheduled, for additional observation. The necessity of continued observation will be constantly reviewed by the Investigator, and the event will be reported to the Sponsor's pharmacovigilance group, or delegate.
- **Follow-up Visits (for 12 weeks postdose):**
 - **Psychedelic Integration Sessions:** Patients will have at least 3 integration sessions over the 2 weeks following their dose to discuss their experience with the therapists. The psychedelic integration sessions will be audio recorded for safety and quality assurance purposes.
 - **Relapse Prevention Psychotherapy:** Patients will have weekly sessions following the dose of BPL-003 as defined in the AUD Therapy manual (can be either face to face or remote) with an AUD therapist (see [Appendix 4](#) for details).

The following timing deviations will **not** be regarded as protocol deviations.

TABLE 4: ACCEPTABLE DEVIATION TIMES

Procedure	Timepoint	Acceptable deviation
Preparation Visit	Days -12 & -7	+/- 5 days
Preparation visit	Day -3	+ 2 days
PK blood sampling	Day 0 – Postdose	+5 min of the scheduled time
Vital signs	Day 0 – Predose	before dosing
	Day 0 – Postdose	±5 min of the scheduled time
Readiness for Discharge questionnaire	Day 0 – Postdose	±5 min of the scheduled time
Integration visit	Follow up days 1, 7, 14	+/- 2 days
Follow up visit	Follow up days 21 - 84	+/- 4 days

6.7. Patient Lifestyle Restrictions

Patients will fast (no food or drink, except water) for at least 8 hours before laboratory blood safety at Screening. On Day 0, patients should be given a light, low-fat breakfast (such as water and fruit) at least 2 hours before dosing.

No food or drink containing poppy seeds will be allowed from 2 weeks before dosing until the Follow-up Visit.

No HDD will be allowed from 72 hours before dosing, and no alcohol at all in the 24 hours prior to dosing.

No recreational drugs will be allowed from Screening until the final Follow-up Visit.

Patient contraceptive requirements are described in [Section 6.2.4](#).

Patients must abstain from smoking, if applicable, while resident on the ward on the day of drug administration as instructed by clinical staff. When permitted, a patient wishing to smoke will be accompanied by clinic staff.

Patients should be accompanied by a responsible adult when released from the clinical study site.

Patients must not drive a car or work with machines for 24 h after dosing.

7. STUDY DRUG MATERIALS AND MANAGEMENT

7.1. Study Drug

BPL-003 will be administered intranasally using the Aptar Unidose (UDS) dry powder delivery system.

Full details of BPL-003 are included in the BPL-003 IB and investigational medicinal product dossier (IMPD).

7.2. Study Drug Packaging and Labeling

BPL-003 has been synthesised by Sterling Pharma Solutions (Dudley, UK) to Good Manufacturing Practice (GMP) standards and prefilled into the Aptar Unidose (UDS) intranasal dry powder delivery device. The device allows a single fixed dose of BPL-003 to be administered intranasally. The dry powder is prefilled into and administered using a standard single unit dose nasal pump device.

Upperton Pharma Solutions (Nottingham, UK) will load the study drug into the Aptar Unidose (UDS) device. Eramol (UK) Ltd (Horley, UK) will label and Qualified Person certify the final patient specific doses, in accordance with GMP and with Eramol (UK) Ltd Manufacturing Authorisation for IMPs (MIA[IMP]).

The fully packaged and labelled BPL-003 will be provided to the study site pharmacy.

7.3. Study Drug Storage

BPL-003 will be stored according to GMP, site SOPs, and a Home Office UK controlled drug licence which is required to possess and supply Schedule 1 drugs.

Details on storage conditions and temperature will be included in the pharmacy manual.

7.4. Administration

BPL-003 will be administered to patients by a trained member of the study team using a single unit dose pump spray. The unit contains only 1 spray, so it should not be tested before use. While the patient is sitting down, he/she should be asked to blow his/her nose to clear the nasal passages. Once the tip of the device is placed into the nostril, the clinic staff will press the plunger to release the dose. Details for administering the dose will be described in a separate study procedures manual.

Dummy UDS devices will be available for demonstration of dosing.

7.5. Study Drug Accountability

It is the responsibility of the Investigator to ensure that a current record of study drug inventory and disposition is maintained at the study site throughout the study. The Investigator, pharmacist, or designee, must keep an accurate record of the quantities of the study drug received, which should match the total quantities of used and unused study drug.

Pursuant to requirements under the Home Office UK Schedule 1 controlled drug licence, a strict audit trail of drug dispensing and usage will be kept. If a patient elects not to take the treatment

on the Dosing Visit, then the study team will return the dose to the site pharmacy, who will arrange quarantine and/or secure destruction in accordance with regulations.

7.6. Study Drug Handling and Disposal

Unused study drug will be destroyed locally per site SOPs or returned to a location designated by BPL or designee. Destruction of study drug should not occur until the end of the study, unless otherwise authorised by BPL or designee. If the study drug is to be destroyed locally, it is the Investigator's responsibility to ensure that arrangements have been made for disposal; that destruction certificates are filed; and that the applicable local regulations, guidelines, and institutional procedures are followed.

At the end of the study, all unused BPL-003 supplies will be returned to the Sponsor or destroyed in accordance with the Sponsor's instructions.

8. PHARMACOKINETIC ASSESSMENTS

There will be three blood draws after dosing on Day 0 to determine the plasma concentration of 5MeO-DMT and its metabolites. The blood draw will be done at 5, 15 and 60 minutes post dose (+5 minutes at each timepoint). The blood will be drawn from the venous catheter previously inserted for the predosing draws for the other laboratory assessments.

Plasma samples will be separated into a primary and backup aliquot and frozen at about -70°C (or below) within 2 hours after collection, and stored until dispatched to Analytical Services International (ASI), St George's Hospital Medical School, University of London, London.

All samples will be analysed at the end of the study as a single batch.

Sample collection, processing and shipping instructions will be included in a separate Study Manual.

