After completing the screening period, those patients who are confirmed as eligible will participate in a minimum of 3 preparatory psychological support sessions over approximately 2 weeks before the BPL-003 treatment session. These sessions will be conducted by a therapist with psychedelic knowledge and an AUD therapist. The last of the 3 sessions will be conducted at the clinic where the dosing will occur so that patients can become familiar with the dosing room, clinic staff and a practice run with the nasal delivery system can be completed. Baseline assessments will be completed on the BPL-003 treatment day, before BPL-003 administration. BPL-003 will be administered on the treatment day in accordance with established safety practices for psychedelic research. A minimum of 3 integration sessions will occur over approximately 2 weeks after the treatment session, together with AUD relapse prevention psychotherapy that will guide the patient through the 12-week postdose follow-up period.

If triggered by the sponsor, a Safety Review Committee (SRC) will decide upon continuation of the study at the 10 mg dose or escalation to 12 mg. The SRC will comprise of, as a minimum, one Investigator (or delegate), the Sponsor's medical monitor, and the Chief Medical Officer (or delegate). The SRC will review, as a minimum, safety, tolerability, PK and PD data up to Day 1 from at least 3 patients dosed with 10 mg BPL-003 in Cohort 1. The dose may be escalated to 12 mg only if the safety, tolerability, PK and PD at 10 mg are deemed acceptable by the SRC. Dose decisions will be documented before further dosing. Additional SRC meetings may be scheduled as required.

The study visits and procedures are outlined below:

- **Screening:** Patients will be screened up to 14 days before their psychedelic preparation session to confirm their eligibility for the study.
- **Abstinence:** Patients will be expected to have no HDD in the 72 hours prior to dosing, and no alcohol in the last 24 hours. If breath alcohol is not zero on dosing day, patients may reschedule once if they are deemed not to have completely relapsed; however, if they fail the second time, they will be excluded from the study.

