In this study, patients will receive a single dose of 10 mg BPL-003 in Cohort 1. As this is the first study of BPL-003 in this patient population, it is unknown how the pharmacodynamic effects in patients with AUD may compare to those seen in healthy volunteers. Data from a pilot study of psilocybin for patients AUD suggested a lower level of acute subjective response (as measured by the MEQ) compared to the response seen in healthy volunteers with comparable doses (Bogenschultz, 2015). Therefore, a potential optional second cohort has been included to provide the option of studying a 12 mg dose should the SRC consider this to be appropriate.

The sponsor may trigger an SRC to evaluate continuation of the study at the 10 mg dose or dose escalation to 12 mg (Cohort 2). The SRC will comprise, as a minimum, of one Investigator [or delegate], the Sponsor’s medical monitor and the Chief Medical Officer [or delegate]. The SRC will review, as a minimum, safety, tolerability, PK and PD data up to Day 1 from at least 3 patients dosed with 10 mg BPL-003 in Cohort 1. The dose will be escalated to 12 mg only if the safety, tolerability, PK and PD at 10 mg are acceptable. Dose decisions will be documented before further dosing. Additional SRC meetings may be scheduled as required.

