4.6. Definition of the End of the Study

The end of the study is defined as the final follow-up visit by the last patient. If the sponsor does not choose to trigger an SRC, the study may complete after cohort 1. If the study is terminated prematurely, the study ends when the Sponsor notifies the Investigator in writing that the study has finished, or when the last patient attends the final follow-up visit, whichever is later.

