7.1 Interim analyses

No interim analyses are planned. This is an open label study and data will be reviewed on an ongoing basis by the Sponsor. In addition, data will be reviewed by the SRC before dose escalation.

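### If a Safety Review Committee is triggered, it must review PK before any dose decision, but the single end-of-study assay leaves no PK result for it to review

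*Protocol*

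**What the plan says.** **What the SRC needs.** The Synopsis (Study Design) and Section 4.3 of the protocol set the same minimum data set: "The SRC will review, as a minimum, safety, tolerability, PK and PD data up to Day 1 from at least 3 patients dosed" at 10 mg in Cohort 1. Acceptable PK is then a condition for moving up. Section 4.3 puts it as "The dose will be escalated to 12 mg only if the safety, tolerability, PK and PD at 10 mg are acceptable", and the Synopsis as "only if the safety, tolerability, PK and PD at 10 mg are deemed acceptable by the SRC". On timing, Section 4.3 adds: "Dose decisions will be documented before further dosing". SAP Section 5 repeats the minimum data set, the condition and the timing. SAP Section 7.1 plans no interim analysis but says that "data will be reviewed by the SRC before dose escalation".

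**When PK results will exist.** Protocol Section 8 schedules draws at 5, 15 and 60 minutes after dosing and freezes the plasma. On the assay it says: "All samples will be analysed at the end of the study as a single batch". Section 4.6 supplies the definition: "The end of the study is defined as the final follow-up visit by the last patient".

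**What is optional.** Under the Synopsis and Section 4.3 the SRC meets only if the sponsor calls it, and Section 4.3 describes the 12 mg cohort as optional. Section 4.6 allows the study to finish after Cohort 1 when no SRC is called.

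**The concern.** The escalation text makes PK both part of what the SRC must see and part of what it must find acceptable, before anyone else is dosed. The assay text produces the first PK result only after everyone has been dosed and followed up. A site or sponsor following the protocol to the letter cannot satisfy both.

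This is the only dose-escalation decision in the study, and PK is one of four named conditions for it (safety, tolerability, PK, PD). An ethics committee or regulator reading Section 4.3 would take it that exposure in patients with alcohol use disorder is checked before 12 mg is given. The schedule in Section 8 does not deliver that check. If an SRC is held, the sponsor must depart from one section or the other, and nothing in the documents says which departure was intended or how it would be recorded.

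**Working it through.** The plan states no figure to reproduce. The check compares the order of events and then counts the PK results available.

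**1. Inputs**

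| Item | Value | Source |
|---|---|---|
| Cohort 1 patients whose PK the SRC must review | at least 3 | Protocol Synopsis and 4.3; SAP 5 |
| Data cut for that review | Day 1 | same |
| PK draws per patient | 3 (5, 15, 60 min) | Protocol 8 |
| Assay timing | one batch, end of study | Protocol 8 |
| End of study | last patient's final follow-up | Protocol 4.6 |
| Final follow-up visit | Day 84, window ±4 days | Protocol Tables 1 and 4 |

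**2. Order required by the escalation text.** At least 3 Cohort 1 patients dosed → PK to Day 1 reviewed → decision documented → further dosing.

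**3. Order given by Sections 8 and 4.6.** All patients dosed → last patient's final follow-up, 84 − 4 = Day 80 to 84 + 4 = Day 88 after that patient's dose → PK assayed.

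**4. Count.** At any SRC meeting that can still affect a dose, the patients with a PK result number 0, against a required minimum of 3. The samples drawn but unread number at least 3 patients × 3 draws = 9. Neither figure depends on cohort size.

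**5. Does this rest on the Section 4.6 definition?** No. Suppose Section 8 uses the phrase more loosely, for example to mean the end of dosing. The sentence still puts every sample into one batch. Patients not yet dosed have no samples, so a batch of all samples cannot have been run while the SRC can still influence a later dose. This is also true of an SRC that considers only continuing at 10 mg, because the minimum data set applies to the review itself.

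**6. Is there an earlier assay elsewhere?** None was found.
- Section 8 splits plasma into primary and backup aliquots but assigns neither to an early run. It refers to a Study Manual for how samples are taken, handled and sent, not for when they are assayed.
- SAP Section 7.1 mentions continuous sponsor review of open-label data, which does not create a concentration that has not been measured.
- SAP Sections 15 and 15.1 cover listings, summaries and plots only.
- SAP Section 17 records one change from the protocol, on laboratory flags.

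**7. When does the conflict apply?** Only if the sponsor triggers an SRC. Without one, the single batch is an ordinary PK plan and nothing conflicts.

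**The case against.** The strongest reply has four parts.

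*The SRC and Cohort 2 are optional, and escalation may not have happened.* This stands. SAP Section 11.1 lists a single treatment group, 10 mg, and the table shells show one treatment column. However, SAP Section 5 still describes both doses and the PK condition, and SAP Section 10 still speaks of comparing ascending dose levels. The rule is therefore still live in the text, even if it was never used.

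*The sponsor could simply assay the Cohort 1 samples early.* This also stands, and it limits the claim. A reader might infer that the PK condition can never be met or that Cohort 2 cannot open. The documents do not support that. An early run would satisfy Section 4.3 and depart only from the batching sentence in Section 8. What the documents do support is narrower: the two sections cannot both be followed once an SRC is called.

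*The safety stakes are modest.* Largely fair. Sections 1.4.2.3.1 and 4.3 report that 12 mg was given in the Phase 1 study, that PK was approximately dose linear from 2.5 to 12 mg, and that no dose passed the preclinical exposure limits. Section 4.3 justifies the second cohort by uncertainty about pharmacodynamic response, and PK is an exploratory endpoint. Safety, tolerability and questionnaire data to Day 1 would be available. A reader might infer that patients would be exposed to an unsafe dose; nothing in the documents supports that. Against this, the Phase 1 table shows only 5 healthy volunteers at 12 mg, and the protocol chose to require PK from patients as well.

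*It is probably a drafting leftover.* Plausible. The summary of changes shows the optional second cohort entering at version 5.0, so the batching sentence may date from a one-cohort design. That is an inference, and it would explain the conflict without removing it.

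**Conclusion.** The contradiction is real but conditional. If the sponsor triggers an SRC, the Synopsis, Section 4.3 and SAP Section 5 require PK from at least 3 Cohort 1 patients, while Section 8 ensures that results exist for 0 of them at any meeting that could still affect dosing. No statistical result changes: the study tests no hypothesis and has no formal sample size. The defect lies in the stated basis for a dose decision.

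The conclusion rests on reading Section 8 as written and on there being no assay schedule in a manual outside the two documents. The practical effect may be small, because Cohort 2 is optional and the SAP lists only 10 mg. The documents do not show whether an SRC met, so it cannot be concluded that any escalation took place without PK.

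**What to change.** Reconcile the protocol Synopsis, Section 4.3 and Section 8 with SAP Sections 5 and 7.1, so that the timing of the PK assay and the SRC's minimum data set agree. Which of the conflicting rules should stand is for the sponsor and investigators to decide; this review does not propose one.

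If an SRC has met or does meet, its minutes and the study report should state which data it had for each patient reviewed, including whether any PK result was available. If no SRC was triggered, one sentence in the study report saying so closes the point.

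The cost is a wording amendment to the protocol with a matching SAP edit, and one additional assay run if the reconciled text calls for it. No extra patients, visits or blood draws are needed.
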